9.3 Ethics and regulatory review

An EC must approve or give a favourable opinion in writing the final study protocol, including the final version of the Informed Consent Form and any other written information to be provided to the patients. The investigator will ensure the distribution of these documents to the applicable EC, and to the study site staff.

The investigator must submit written approval to PAREXEL before he or she can enrol any patient into the study. Following approval, the protocol and amendment(s) will be submitted to the IND under which the study is being conducted, according to local requirements.

The EC must approve all advertising used to recruit patients for the study.

PAREXEL must approve any modifications to the Informed Consent Form that are needed to meet local requirements.

Before enrolment of any patient into the study, the final study protocol, including the final version of the Informed Consent Form, is approved by the national regulatory authority or a notification to the national regulatory authority is done, according to local regulations.

The distribution of any of these documents to the national regulatory authorities will be handled by AstraZeneca or PAREXEL as appropriate.

AstraZeneca will provide ECs and principal investigators with safety updates/reports according to local requirements.

The principal investigator is also responsible for providing the EC with reports of any serious and unexpected adverse drug reactions from any other study conducted with the IP. AstraZeneca will provide this information to the principal investigator.

Progress reports and notifications of serious and unexpected adverse drug reactions will be provided to the EC according to local regulations and guidelines.

Where there is genetic and/or/biomarker research, approval must be obtained for this genetic and/or biomarker research, respectively, and the associated informed consents from the EC. It must be clearly stated in the approval that this genetic and/or biomarker research is approved. The investigator must submit written approval to PAREXEL before any patient participates in this genetic and/or biomarker research.

9.4 Informed consent

The principal investigator(s) at each centre will ensure that the patient or his/her legally authorised representative is given full and adequate oral and written information about the nature, purpose, possible risk and benefit of the study. Patients or their legally authorised representative must also be notified that they are free to discontinue from the study at any time. The patient or his/her legally authorised representative should be given the opportunity to ask questions and allowed time to consider the information provided.

The patient's or his/her legally authorised representative's signed and dated informed consent must be obtained before conducting any procedure specifically for the study. Country and/or local EC requirements for acceptable methods of obtaining signed and dated informed consent will be followed (such as acceptability of Fax).

The principal investigator(s) must store the original, signed Informed Consent Form. A copy of the signed Informed Consent Form must be given to the patient or his/her legally authorised representative.

The genetic and biomarker research is optional and the patient may participate in the main study without participating in the genetic and/or biomarker component. Patients (or their legally authorised representative) who agree to take part in this genetic research will be asked to sign a separate Informed Consent Form to confirm their willingness to have this sample taken. Patients (or their legally authorised representative) who agree to take part in the biomarker research will be asked to sign either a separate Informed Consent Form or note consent in a specific section of the general Informed Consent Form to confirm their willingness to have this sample taken.

To participate in the genetic component of the study the patient or his/her legally authorised representative must sign and date both the consent form for the main study (non-genetic/biomarker components of the study) and a consent form for each of the genetic and biomarker components of the study. Copies of all signed and dated consent forms must be given to the patient or his/her legally authorised representative and the original filed at the study centre. The principal investigator(s) is responsible for ensuring that consent is given

freely and that the patient or his/her legally authorised representative understands that they may freely discontinue the genetic and/or biomarker aspects of the study at any time.

If modifications are made according to local requirements, the new version of either consent has to be approved by PAREXEL and the EC.

Those patients who are unconscious or considered by the investigator clinically unable to consent at screening and who are entered into the study by the consent of a legally acceptable representative should provide their own written informed consent for continuing to participate in the study as soon as possible on recovery, as applicable in accordance with local regulations.

9.5 Changes to the protocol and informed consent form

Study procedures will not be changed without the mutual agreement of the co-ordinating investigator and PAREXEL.

If there are any substantial changes to the study protocol, then these changes will be documented in a study protocol amendment and/or a new version of the study protocol (Amended Protocol).

The amendment must be approved by each EC and if applicable, also the national regulatory authority, before implementation. Local requirements must be followed for amended protocols.

AstraZeneca will distribute any subsequent amendments and new versions of the protocol to each principal investigator(s). For distribution to EC see Section 9.3.

If a protocol amendment requires a change to a centre's Informed Consent Form, AstraZeneca and the centre's EC must approve the revised Informed Consent Form before the revised form is used.

If local regulations require, any administrative change will be communicated to or approved by each EC.

9.6 Audits and inspections

Authorised representatives of AstraZeneca, PAREXEL, a regulatory authority, or an EC may perform audits or inspections at the centre, including source data verification. The purpose of an audit or inspection is to systematically and independently examine all study-related activities and documents, to determine whether these activities were conducted, and data were recorded, analysed, and accurately reported according to the protocol, GCP, guidelines of the ICH, and any applicable regulatory requirements. The investigator will contact PAREXEL immediately if contacted by a regulatory agency about an inspection at the centre.

Investigators must allow direct access to all source data and source documents in the event of such an inspection.

10. STUDY MANAGEMENT BY ASTRAZENECA

10.1 Pre-study activities

Before the first patient is entered into the study, it is necessary for a representative of PAREXEL to visit the investigational study site to:

- Determine the adequacy of the facilities and to verify qualifications of each investigator and associated staff.
- Discuss with the investigator(s) (and other personnel involved with the study) their responsibilities with regard to protocol adherence, investigator responsibilities, procedures for ensuring adequate and correct documentation, and the responsibilities of AstraZeneca or its representatives, including those from PAREXEL. This will be documented in a CSA between AstraZeneca and the investigator.

10.2 Training of study site personnel

Before the first patient is entered into the study, a PAREXEL representative will review and discuss the requirements of the Clinical Study Protocol and related documents with the investigational staff and also train them in any study specific procedures and the WBDC system utilised.

The principal investigator will ensure that appropriate training relevant to the study is given to all of these staff, and that any new information relevant to the performance of this study is forwarded to the staff involved.

The principal investigator will maintain a record of all individuals involved in the study (medical, nursing and other staff).

10.3 Monitoring of the study

During the study, a PAREXEL representative will have regular contacts with the study site, including visits to:

- Provide information and support to the investigator(s).
- Confirm that facilities remain acceptable.
- Confirm that the investigational team is adhering to the protocol that data are being accurately and timely recorded in the eCRFs, and that IP accountability checks are being performed.
- Perform source data verification (a comparison of the data in the eCRFs with the patient's medical records at the hospital or practice, and other records relevant to the study) including verification of informed consent of participating patients.

Investigators must allow direct access to all original records for each patient (eg, clinic charts).

- Ensure withdrawal of informed consent to the use of the patient's biological samples is reported and biological samples are identified and disposed/destroyed accordingly, and the action is documented, and reported to the patient.

The PAREXEL representative will be available between visits if the investigator(s) or other staff at the centre needs information and advice about the study conduct.

10.3.1 Source data

Refer to the CSA for location of source data.

10.4 Study agreements

The principal investigator at each centre must comply with all the terms, conditions, and obligations of the CSA, or equivalent, for this study. In the event of any inconsistency between this Clinical Study Protocol and the CSA, the Clinical Study Protocol shall prevail with respect to the conduct of the study and the treatment of patients and in all other respects, not relating to study conduct or treatment of patients, the terms of the CSA shall prevail.

Agreements between AstraZeneca and the principal investigator must be in place before any study-related procedures can take place, or patients be enrolled.

10.4.1 Archiving of study documents.

The investigator follows the principles outlined in the CSA.

10.5 Study timetable and end of study

The end of the entire study is defined as “the last visit of the last patient undergoing the study”.

The study may be terminated at individual centres if the study procedures are not being performed according to GCP, or if recruitment is slow. AstraZeneca may also terminate the entire study prematurely if concerns for safety arise within this study or in any other study with AZD9773. If AstraZeneca decides to prematurely terminate or suspend the study, PAREXEL, the investigators and regulatory authorities must receive written notification of the reasons for the premature termination or suspension. The investigators will immediately notify the decision to the patients, give appropriate medical treatment, take necessary measures, and record treatment or measures provided on the source documents.

11. DATA MANAGEMENT

A WBDC system will be used for data collection and query handling. The investigator will ensure that data are recorded on the eCRFs as specified in the study protocol and in

accordance with the instructions provided. The investigator ensures the accuracy, completeness, and timeliness of the data recorded and of the provision of answers to data queries according to the CSA.

Clinical data will be sent in a secured validated format to PAREXEL Data Management on an ongoing basis. However, as the PK data would unblind the study, these data will not be transferred to PAREXEL Data Management until database lock has been declared. All processes will be documented in the PAREXEL Data Management study files.

Data will be entered in the WBDC system at the study site. Trained study personnel will be responsible for entering data on the observations, tests and assessments specified in the protocol into the WBDC system and according to the eCRF instructions. The eCRF instructions will also provide the study site with data entry instructions. A monitor from PAREXEL will visit the investigational site and review the eCRFs. Data entered in the WBDC system will be immediately saved to a central database and changes tracked to provide an audit trail. When data have been entered, reviewed, edited and Source Data Verification performed the investigator will be notified to sign the eCRF electronically as per the agreed project process and data will be locked to prevent further editing. A copy of the eCRF will be archived at the study site. eCRF records of SAEs will be reconciled against reports made to AstraZeneca Drug Safety.

Raw data collected by third party vendors (cytokines, procalcitonin, troponin I, protein C activity, ECGs, PK analyte concentration measurements, HASA Igs and total HASA bridging assay, NAB assays) will be electronically transferred to PAREXEL Data Management for inclusion in the PAREXEL Data Management study database.

Data verification and data validation checks will be performed by PAREXEL Data Management utilising electronic edit checks comprised of validated computer programs and manual data review. Any data discrepancies will be referred back to the investigator via the site monitor. A clean database will be declared by PAREXEL Data Management after consistency checks have been run, all SAE reconciliations have been resolved, all data in a clean data transfer have been received including third party vendor data, all the data in the database has been accounted for, all edit checks have been run and data discrepancies have been resolved or accepted and a Quality Check on a sample of the data has been performed. After the database has been declared clean it will be locked and editing in the database will only be allowed with the proper documentation. Further details of how the 2 database locks will be handled will be described in the SAP.

After database lock, data will be extracted to SAS[®] (SAS Institute, Inc., Cary, NC) for analysis as defined in the SAP. SAEs will be entered into the global AstraZeneca safety database.

AEs and prior and concomitant diseases will be coded according to the version of MedDRA agreed with AstraZeneca. Concomitant medications will be coded using the AstraZeneca drug dictionary.

In the case of genetic and/or biomarker research, only the date the patient gave consent to participation in the genetic and/or biomarker research and the date the blood sample was taken from the patient will be recorded in the eCRF and database.

Data associated with biological samples will be transferred to laboratories internal or external to AstraZeneca.

The analysis of the multiplex assay for exploratory chemokines and the plasma renal panel for exploratory analysis are not planned to be included in the Clinical Study Report for this study.

Genotype data generated in this study will be stored in the AstraZeneca genotyping LIMS database, or other appropriate secure system, separate from the database used for the main study.

Some or all of the clinical datasets from the main study may be merged with the genetic data in a suitable secure environment separate from the clinical database. The results from this genetic research will be reported separately from the Clinical Study Report for the main study.

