4.2 Rationale for study design, doses and control groups

In a Phase IIb study conducted with D-CytoFab employing a loading dose of 250 units/kg followed by 9 doses of 50 units/kg every 12 hours, there was a significant, prompt and sustained suppression of plasma TNF α during treatment such that TNF α was undetectable in nearly all plasma samples obtained during the entire 5 days of active treatment. Modest and transient rises of TNF α in the treated group occurred in only 2 patients. These 2 patients had the highest baseline TNF α levels of the group, suggesting that dosing was in the optimal region. This dosing regimen was found to significantly improve clinical outcomes for the D-CytoFab-treated group with no adverse safety findings.

In a recently completed Phase IIa study (D0620C00004) conducted with AZD9773, similar effects on plasma TNF α were seen. This particular study was not powered to detect efficacy, but did demonstrate that loading doses of up to 750 units/kg and maintenance doses of up to 250 units/kg every 12 hours were well tolerated in patients with severe sepsis.

In this Phase IIb study, which is powered to detect an effect on the parameter of VFD as a measure of efficacy, both the 250/50 units/kg regimen and the 500/100 units/kg regimen will be evaluated to determine which dose regimen should be employed in further clinical studies to evaluate an effect of AZD9773 on 28-day mortality. Both of these dose regimens were well tolerated in the Phase IIa (D0620C00004) study and the 250 units/kg dose was also well tolerated in the earlier D-CytoFab study. A dose regimen lower than 250/50 units/kg was not included in this Phase IIb study because 250/50 units/kg produced significant clinical benefit with D-CytoFab and there is currently no tolerability concern with the doses chosen for this study. The higher dose will explore the possibility of increased benefit with more TNF α suppression and help define the therapeutic dose-response.

The optimal duration of therapy with an anti-TNF α agent is a balance between intervening to suppress TNF α bursts while not inhibiting the host inflammatory response for too long. A treatment period of 5 days was chosen for the Phase IIb study of D-CytoFab and for the recently completed Phase IIa study (D0620C00004) conducted with AZD9773. In this Phase IIb study the maximum treatment period will also be 5 days.

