13. STATISTICAL METHODS AND SAMPLE SIZE DETERMINATION BY ASTRAZENECA

13.1 General principles

A comprehensive SAP will be finalised before the last patient visit. All statistical analyses will be performed by PAREXEL. Any deviations from those analyses presented here and/or in the SAP will be detailed in the clinical study report. All outputs will be produced using SAS[®] version 9 or later in accordance with AstraZeneca standards.

All study data will be analysed after the 28-day follow up is complete for all patients. A further analysis will be performed using the Day 90 assessment to understand longer-term patient outcomes (survival and HRQoL).

The following efficacy endpoints will be subject to formal statistical analysis: VFDs, 7-day mortality, 28-day mortality, mortality at Day 90, organ failure-free days, shock-free days and ICU-free days. All other data will only be summarised.

All efficacy data will be summarised and analysed using the per protocol (PP) population. Additionally, an ITT analysis of the endpoints listed above for formal analysis will also be undertaken using the ITT population.

For each of the endpoints subject to statistical analysis the following statistical comparisons will be performed: AZD9773 dose 1 versus placebo, AZD9773 dose 2 versus placebo, and combined AZD9773 dose arms 1 and 2 versus placebo. Although there are three primary comparisons, this is an exploratory Phase IIb study and consequently no adjustment for multiple comparisons will be made.

Unless stated below, no imputation of missing data will be performed. All data recorded on the database will be included in data listings. Any spurious or erroneous data will be queried and followed up until satisfactorily resolved.

The nominal significance level used for this study will be 10% one-sided. However, it is important to note that the study has only been sized based on VFDs over 28 days; this study is not powered to detect a statistically significant difference in 7-day mortality, 28-day mortality or mortality at Day 90. In this case the confidence intervals (CIs) will provide a guide to the possible range of the true treatment effect. This may also be the case for the other secondary endpoints.

Demography data will be summarised using the PP and ITT populations and safety data will be summarised using the safety population. For all summaries of change from baseline, baseline is defined as the latest non-missing assessment prior to first study drug infusion.

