13.2.3 Per-Protocol population

This population will be a subset of the ITT population including only patients without important detected protocol deviations affecting the efficacy endpoints. Patients will be summarised according to the actual treatment first received.

The patients with important protocol deviations will include those failing the inclusion/exclusion criteria as well as any patients taking medications that are prohibited during the study treatment period (see Section 6.5.2). Prior to clean file and code break, the patients to be excluded from the PP population will be reviewed and agreed by the study team physician and statistician.

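### Only PK data are embargoed as unblinding, yet on-treatment TNF-alpha also points to active drug and must be received before lock, in the period when per-protocol exclusions are agreed

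*Protocol*

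**What the plan says.** Section 11 sets the default flow: "Clinical data will be sent in a secured validated format to PAREXEL Data Management on an ongoing basis". It then makes a single exception: "as the PK data would unblind the study, these data will not be transferred to PAREXEL Data Management until database lock".

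The same section lists what outside laboratories send: "Raw data collected by third party vendors (cytokines, procalcitonin, troponin I, protein C activity, ECGs, PK analyte concentration measurements", continuing "HASA Igs and total HASA bridging assay, NAB assays) will be electronically transferred to PAREXEL Data Management". No timing limit is attached to the cytokine, HASA or neutralising-antibody (NAB) results. Among the conditions for a clean database is that "all data in a clean data transfer have been received including third party vendor data"; lock comes after that.

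Section 13.2.3 times the per-protocol decisions: "Prior to clean file and code break, the patients to be excluded from the PP population will be reviewed and agreed". The decision-makers are the study team physician and statistician. Section 13.1 gives that population its role: "All efficacy data will be summarised and analysed using the per protocol (PP) population". ITT is an additional analysis of the formally tested endpoints.

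On TNF-alpha, Section 4.2 reports that in the D-CytoFab Phase IIb study it "was undetectable in nearly all plasma samples obtained during the entire 5 days of active treatment". The same section says that nearly all treated patients in that study and in the AZD9773 Phase IIa study had undetectable levels during dosing, with mean levels back to those of placebo recipients within 48 hours of the last dose. Section 2.1.4 reports that AZD9773 held serum TNF-alpha close to the assay's limit of quantification throughout dosing.

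**The concern.** The protocol embargoes PK because a measured drug concentration shows who received drug. A marker that the drug suppresses in nearly all treated patients carries a weaker form of the same information, but the embargo does not extend to it.

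This matters because of the PP set. Which deviations count as important is partly a matter of judgement, and the set so defined carries the main efficacy analysis. Section 6.3.2 requires sponsor and CRO staff to stay blinded and evaluability decisions to be documented before the code is broken. If someone taking part in those decisions, or in data queries, can see on-treatment TNF-alpha, the decisions are formally blind but open to challenge. What is at stake is mainly the credibility of the PP analysis.

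Section 11 also has a wording conflict. PK concentrations are in the vendor list, vendor data are needed for a clean database, and lock follows the clean declaration; yet PK may not be transferred until lock is declared.

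**Working it through.** **1. Sequence of steps.**

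| Step | Timing in the protocol |
|---|---|
| PK transfer | not until database lock (Section 11) |
| Cytokine, HASA and NAB transfer | no embargo; received before the database is declared clean (Section 11) |
| PP exclusions agreed | before clean file and code break (Section 13.2.3) |
| Lock | after the clean declaration (Section 11) |

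Transfer of TNF-alpha and agreement of the PP exclusions both precede clean file. Neither is ordered against the other, and no text says who may see the results.

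**2. How many TNF-alpha values are exposed.** Section 7.4.2 schedules nine samples: screening, Day 1, Day 2 (twice), and Days 4, 6, 7, 10 and 15. Six fall after the first infusion and up to Day 7. Fewer will be informative in a patient who stops early for improvement, and Day 7 may already be affected by the post-dose rebound.

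**3. How informative TNF-alpha could be.** The documents give no placebo detection rate, so the rates here are assumptions. Let *a* be the proportion of active patients with undetectable on-treatment TNF-alpha (0.90 to 0.98) and *p* the same proportion on placebo (0.20 to 0.80). With 1:1:1 allocation there are two active patients for each placebo patient.

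- P(active | undetectable) = 2a / (2a + p). Lowest: 1.80 / (1.80 + 0.80) = 0.69. Highest: 1.96 / (1.96 + 0.20) = 0.91. Prior: 2/3 = 0.67.
- P(placebo | detectable) = (1 − p) / [(1 − p) + 2(1 − a)]. Lowest: 0.20 / (0.20 + 0.20) = 0.50. Highest: 0.80 / (0.80 + 0.04) = 0.95. Prior: 1/3 = 0.33.

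The marker runs from barely informative about active drug to strongly informative in both directions, depending mainly on *p*. It is not a certain code break anywhere in this range.

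**4. Effect on the estimate.** The plan's sample-size figure reproduces. With SD 11.380 and 100 per group, the standard error of a difference is 11.38 × √(2/100) = 1.61. A 4.2-day difference at 10% one-sided gives 90.8% power against the stated 90%, and 97 per group would suffice.

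Removing one patient with zero ventilator-free days from an arm of 100 with mean *m* raises that arm's mean by m/99. With the earlier trial's means in Section 2.4:

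- m = 9.8: 9.8/99 = 0.10 day
- m = 15.0: 15.0/99 = 0.15 day

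That is 0.10/4.2 to 0.15/4.2, about 2% to 4% of the target difference, and 0.10/1.61 to 0.15/1.61, about 0.06 to 0.09 of a standard error, per selective exclusion.

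**The case against.** The strongest reply is that receipt is not access. The results go to data management; a physician and a statistician decide PP membership, and no text gives them the results. Data are extracted for analysis only after lock, Section 6.3.2 requires staff to remain blinded, and access controls could sit in the data management files or the SAP, which are not at hand. This stands as a limit on the claim. A reader might infer that the results reach the decision-makers before the exclusions are settled; the documents permit that order but do not state it. The reply does not remove the point, because Section 11 itself decides which data are withheld as unblinding and names only PK.

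A reader might also infer that HASA and NAB results reveal treatment. The documents do not support this. Section 4.2 treats HASA induction as a question the study will answer, and no NAB positivity rate is given. A new positive might suggest active drug; a negative would not identify placebo.

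A third tempting reading is that most active patients could be identified from TNF-alpha. That cannot be derived without the placebo detection rate and the share of patients with measurable baseline values.

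It is fair to add that the PP exclusion grounds named in Section 13.2.3, eligibility failures and prohibited medication, are largely checkable facts, and that an ITT analysis of the same endpoints would help expose selective exclusion. Both reduce the risk.

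On the PK wording, the specific exception can be read as overriding the general vendor-data condition, and Section 11 leaves handling of the two locks to the SAP. That makes it a clarification, but the literal text still cannot be satisfied.

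**Conclusion.** The point holds in limited form. The protocol's reason for embargoing PK applies, with less certainty, to on-treatment TNF-alpha, which is left unrestricted through the period in which the main efficacy set is fixed. This rests on the suppression reported in Sections 2.1.4 and 4.2 carrying over to this study, and on no separation of access being stated in the protocol.

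The documents do not show that blinding will be compromised. The numerical effect is likely small, 0.10 to 0.15 day per selective exclusion under the earlier trial's means, so many such exclusions would be needed to change the result. It is a cheap improvement worth making, mainly to keep the PP decisions defensible as blind.

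**What to change.** Amend Section 11 in two places.

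- **Embargo.** Withhold post-baseline TNF-alpha along with PK until PP membership is documented and the database is locked. Alternatively, transfer it under scrambled patient identifiers or to named staff with no part in queries or PP decisions. Treat post-dose HASA and NAB results the same way as a precaution. Baseline TNF-alpha may transfer as planned, since it precedes treatment.
- **Clean-database condition.** Exempt all embargoed data, including PK, from the requirement that vendor data be received before the database is declared clean. This also removes the literal conflict over PK.

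The cost is new wording and revised data-transfer agreements; no patient procedure changes. The drawback is that reconciliation of these results moves to just after lock. Dummy transfers beforehand can test the file structure.
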